4 STATISTICAL ANALYSES

4.1 GENERAL CONSIDERATIONS

In general, continuous data will be summarized using the number of observations available, mean, standard deviation (SD), median, minimum, and maximum. Categorical and ordinal data will be summarized using the count and percentage of participants. Time to event variables will be analyzed using the Kaplan-Meier method.

The baseline value is defined as the last available value before the first dose of IMP. For participants enrolled but not treated, the baseline value is defined as the last available value before enrollment.

Analyses will be performed by cohort (and overall) within Phase 2, for demographics and baseline characteristics. If Phase 1 dose level is reduced due to unacceptable toxicities, summaries may also be performed on Phase 1 participants, by dose level group.

Observation period

The observation period will be divided into 3 segments:

- The **pre-treatment period** is defined as the time from when the participants give informed consent to first IMP administration.
- The **on-treatment period** (ie, treatment-emergent [TE] period) is defined as the period from the first IMP administration to the last IMP administration + 30 days.
- The **post-treatment period** is defined as the time starting 31 days after the last dose of IMP to study cut-off.

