6.7 INTERVENTION AFTER THE END OF THE STUDY

The IMP will not be provided after the end of the treatment period. The participant's treatment after study discontinuation will be at the discretion of the treating physician.

For participants who received isatuximab treatment and subsequently proceed to solid organ transplantation, it is recommended to include the following as part of the post-transplant immunosuppression regimen:

- Anti-thymocyte globulin (rabbit) as indicated for prophylaxis of acute rejection.
- Steroids during maintenance phase, with tapering if applicable.

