In the case of participants discontinuing IMP during treatment period due to transplantation, the participants should complete an E/D visit (30 ± 7 days after last IMP) if clinically feasible, and proceed to extended FUP.

All cases of definitive intervention discontinuation must be recorded by the Investigator in the appropriate pages of the eCRF when considered as confirmed.

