9.4.2 Safety analyses

All safety analyses will be performed on the Safety Evaluable Population for Phase 1 and All Treated Population for Phase 2.

For safety analyses, the observation period will be divided into 3 segments:

- The pretreatment period is defined as the time from when the participants give informed consent to the first administration of the IMP.

- The on-treatment period is defined as the time from the first dose of IMP up to 30 days after the last dose of IMP.
- The post-treatment period is defined as the time starting 31 days after the last dose of IMP to study cut-off.

Analyses of adverse events

Adverse events will be coded according to Medical Dictionary for Regulatory Activities (MedDRA) and graded according to NCI-CTCAE (version 5.0 criteria).

An overall summary of TEAEs will be provided. The number (%) of participants experiencing TEAEs by primary system organ class (SOC) and preferred term (PT) will be summarized by CTCAE grade (all grades and Grade ≥ 3). Similar summary tables will be generated for treatment related TEAEs, AESIs, TEAEs leading to treatment discontinuation, serious TEAEs, and TEAEs with fatal outcome. Post-treatment AEs will be analyzed separately.

Clinical laboratory evaluations

All laboratory abnormalities will be graded according to NCI-CTCAE, when applicable. The number (%) of participants with laboratory abnormalities (ie, all grades and grade ≥ 3) will be tabulated using the worst grade during on-treatment period.

Table 10 - Safety analyses

Endpoint	Statistical Analysis Methods
Primary: AEs/SAEs, and laboratory abnormalities in Phase 1	Will be listed
Secondary: AEs/SAEs, and laboratory abnormalities in Phase 2	Will be summarized using descriptive statistics
Exploratory	Not applicable

Abbreviations: AE = adverse event, SAE = serious adverse event

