The study will have a screening period of up to 28 days, a treatment period of up to 12 weeks, a site visit follow-up period (FUP) of up to 26 weeks, and an extended FUP which include telephone contacts every 90 days and information collection until study cut-off, death, or lost to follow-up. The study cut-off is planned at 26 weeks after the last participant completes the treatment period, or when the last ongoing participant is lost to follow-up, whichever is earlier. The Sponsor (Sanofi) may choose to extend the study cut-off date depending on the enrollment rate observed to facilitate adequate follow-up data collection. Participants who wish to proceed to transplantation when a compatible donor becomes available while on study must discontinue IMP immediately, complete an early discontinuation (E/D) visit prior to transplantation if clinically feasible, and proceed to extended FUP. The study duration that involves site visit per participant (ie, screening, treatment, site visit FUP) will be approximately 42 weeks. The study duration including extended FUP per participant will be approximately 78 weeks (depending when the participant is enrolled).

Treatment period: The cycle duration is 28 days and a complete treatment period is comprised of 3 cycles of IMP treatment. Participants will continue treatment until receiving 3 cycles of IMP, unacceptable AE per Investigator's judgment, or participants' decision to stop the treatment.

Site visit FUP: Participants completing the treatment period and who are able to remain on study will return to the study sites for study procedures.

Extended FUP: The following participants will be followed-up every 90 days by phone calls, until study cut-off date, death, or lost to follow-up, whichever comes first:

- Participants who completed or discontinued from site visit FUP
- Participants who proceed to transplantation during treatment period or site visit FUP.

During extended FUP, specified information per protocol will also be collected by study site (see protocol section 1.3).

Below figures show the study schema and duration of study period:

Figure 1 - Graphical study design

[figure not shown]
[figure not shown]

Figure 2 - Duration of study period (per participant)

Details on schedule of activities (SoA) are provided in protocol section 1.3.

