4.7.2 Adverse events

General common rules for adverse events

All AEs will be graded according to National cancer institute common terminology for adverse events [(NCI-CTCAE) version 5.0] and coded to a lower-level term (LLT), preferred term (PT), high-level term (HLT), high-level group term (HLGT), and associated primary system organ class (SOC) using the Medical Dictionary for Regulatory Activities (MedDRA) version currently in effect at Sanofi at the time of database lock.

The AEs will be analyzed in the following 3 categories:

- Pre-treatment AEs: AEs that developed, worsened or became serious during the pre-treatment period.
- Treatment-emergent adverse events (TEAE)s: AEs that developed, worsened or became serious during the on-treatment period
- Post-treatment AEs: AEs that developed, worsened or became serious during the post-treatment period

Similarly, deaths will be analyzed in the pre-treatment, treatment-emergent and post-treatment periods.

The primary focus of AE reporting will be on TEAEs. Pre-treatment and post-treatment AEs will be described separately.

An AE with incomplete or missing date/time of onset (occurrence, worsening, or becoming serious) will be classified as a TEAE unless there is definitive information to determine it is a pre-treatment or a post-treatment AE.

If the assessment of the relationship to IMP is missing for an AE, this AE will be assumed as related to IMP. If the toxicity grade is missing for 1 of the treatment-emergent occurrences of an AE, the toxicity grade will be imputed with the maximal severity of the other occurrences. If the severity is missing for all the occurrences, the toxicity grade will be left as missing.

Multiple occurrences of the same event in the same participant will be counted only once in the tables within a treatment phase, using the maximum (worst) grade by treatment phase. Summaries will be provided for all grades combined and for grade ≥ 3 (including Grade 5). Missing grades, if any, will be included in the “all grades” category.

The AE tables will be sorted as indicated in [Table 5](#).

Table 5 - Sorting of AE tables

AE presentation	Sorting rules
SOC and PT	By the internationally agreed SOC order and decreasing frequency of PTs ^{a, b}
PT	By decreasing frequency of PTs ^a

a Sorting will be based on the overall incidence.

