For laboratory variables, analyses according to NCI grading will be made based on NCI-CTCAE version specified in the protocol. For laboratory variables for which NCI-CTCAE scale is not applicable, potentially clinically significant abnormality (PCSA) summaries may be performed using sponsor or local laboratory normal ranges.

In addition, for vital signs (ie, heart rate, systolic and diastolic blood pressure), PCSA analyses will be performed based on the PCSA criteria listed below.

Vital signs parameter	PCSA criteria
Systolic Blood Pressure (mmHg)	≤ 95 mmHg and decrease from baseline ≥ 20 mmHg ≥ 160 mmHg and increase from baseline ≥ 20 mmHg
Diastolic Blood Pressure (mmHg)	≤ 45 mmHg and decrease from baseline ≥ 10 mmHg ≥ 110 mmHg and increase from baseline ≥ 10 mmHg
Heart Rate (beats/min)	≤ 50 beats/min and decrease from baseline ≥ 20 beats/min ≥ 120 beats/min and increase from baseline ≥ 20 beats/min

Analyses according to PCSA and NCI grading will be performed based on the worst value during the treatment-emergent period, using all measurements (either local or central, either scheduled, nonscheduled or repeated).

For laboratory variables and vital signs above, the incidence of participants with at least one PCSA during the treatment-emergent period will be summarized regardless of the baseline level and according to the following baseline status categories:

- Normal/missing
- Abnormal according to PCSA criterion or criteria

For laboratory variables graded by NCI-CTCAE,

- The number (%) of participants with abnormal laboratory tests at baseline will be presented by grade.
- The number (%) of participants with abnormal laboratory tests during the treatment-emergent period will be summarized by grade. When appropriate, the number (%) of participants with abnormality of any grade and with Grade 3-4 abnormalities will be provided.

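### The safety window runs to last dose + 30 days with no split at transplant, so post-surgical events by day 30 enter the all-causality TEAE tables and, where recorded, the laboratory tables

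*SAP*

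**What the plan says.** SAP 4.1 states that the on-treatment period "is defined as the period from the first IMP administration to the last IMP administration + 30 days". Protocol 9.4.2 gives the same rule: "The on-treatment period is defined as the time from the first dose of IMP up to 30 days after the last dose of IMP". Neither mentions transplantation.

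SAP 4.7.2 defines TEAEs by timing alone, as "AEs that developed, worsened or became serious during the on-treatment period". SAP 4.7.3.1 says that the NCI-grade and PCSA analyses "will be performed based on the worst value during the treatment-emergent period, using all measurements", and it includes unscheduled and repeated values. Under Protocol 8.3.1, AE collection narrows to related or serious events only beyond 30 days after the last dose.

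Transplant during the study is planned for. SAP 1.1 says that participants going to transplant "must discontinue IMP immediately, complete an early discontinuation (E/D) visit prior to transplantation if clinically feasible, and proceed to extended FUP". Up to 6 Cohort A participants may have a living donor. Protocol 6.7 recommends, after transplant, "Anti-thymocyte globulin (rabbit) as indicated for prophylaxis of acute rejection" together with maintenance steroids.

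Table 6 of SAP 4.7.2 has separate tables for TEAEs and SAEs that the investigator judges related. SAP 5.3 summarises post-transplant immunosuppression as medication. We found no safety table in either document that separates data before and after transplant.

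**The concern.** A participant who stops isatuximab for a transplant may have major surgery and lymphocyte-depleting induction while still inside the on-treatment window. Surgical complications, cytopenias and infections from that time are then pooled with events that arose on isatuximab alone. The trial has one arm, so no comparator shows how much of an incidence belongs to surgery and induction.

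Pooling can mislead in two ways. It can raise the all-causality incidence of events that isatuximab did not cause. It can also hide a real post-transplant signal in participants previously given isatuximab. The second matters because Protocol 2.3.2.2 and 2.3.3 name infection and T-cell mediated rejection as specific concerns. The reader of the planned tables could not tell which situation applies.

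**Working it through.** The plan states no figure that depends on this rule, so there is nothing to reproduce. The check covers timing, the routes by which data enter the tables, and scale.

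**Timing.** Three 28-day cycles put the last planned dose (Cycle 3 Day 15) on study day 28 + 28 + 15 = 71. The window closes on day 71 + 30 = 101. Its last 30 days, 30/101 = 29.7% of it, follow the final dose.

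Suppose transplant occurs during dosing, with no dose delay and surgery on the day the organ is accepted. The last infusion is then at most 7 days old in Cycle 1 and at most 14 days old in Cycles 2 and 3. At least 30 − 7 = 23 or 30 − 14 = 16 window days therefore fall after surgery, and at most 30. A transplant after the final dose leaves anything from 30 days down to none.

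**Adverse events.** All AEs to day 30 are collected, and a TEAE needs only onset, worsening or becoming serious in the window. A surgical complication on, say, day 20 after the last dose qualifies. The operation itself does not, because Protocol 10.3 excludes procedures from the AE definition.

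**Laboratory values.** The Schedule of Activities shows no routine chemistry or hematology in extended follow-up, where transplanted participants go. Three routes remain:
- Non-protocol local results that change management or are clinically significant must be recorded (Protocol 8.2.5).
- eGFR is collected with transplant status (Schedule of Activities, footnote o), and SAP 4.7.3.1 lists eGFR for analysis.
- The early-discontinuation (E/D) visit, which includes chemistry and hematology, may fall after surgery.

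On the E/D visit the documents disagree. The Protocol synopsis, Protocol 4.1, footnote b of the Schedule of Activities and SAP 1.1 put it before transplant where feasible. Protocol 7.1.1 says that "the participants should complete an E/D visit (30 ± 7 days after last IMP) if clinically feasible". That covers days 23 to 37, of which days 23 to 30 (8 of 15) lie inside the window.

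**Scale.** Let one participant have an event of a given type only after transplant. The incidence of that type changes by 1/n, shown here with the Clopper-Pearson 95% interval for 1/n:

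| n | Source | 1/n | 95% CI |
|---|---|---|---|
| 12 | minimum per cohort | 8.3% | 0.2 to 38.5 |
| 24 | lower total, starting dose retained | 4.2% | 0.1 to 21.1 |
| 36 | upper total, starting dose retained | 2.8% | 0.1 to 14.5 |

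The documents give no share q of participants transplanted inside the window. For assumed values of q, the chance of at least one is 1 − (1 − q)^n:

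| n | q = 2% | q = 5% | q = 10% |
|---|---|---|---|
| 12 | 21.5% | 46.0% | 71.8% |
| 24 | 38.4% | 70.8% | 92.0% |
| 36 | 51.7% | 84.2% | 97.7% |

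**The case against.** The strongest reply is that an all-causality window of last dose + 30 days is a common convention and the cautious choice in a single-arm study. Ending the main window at transplant would take early infections and rejection out of the main tables, when the protocol names these as risks. It would also depart from Protocol 9.4.2, and the SAP version history records an interim analysis on 26 August 2021, so the main definition would change after a look at data. This stands, and it is why the main window should stay.

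A reader might infer that these events are attributed to isatuximab. The documents do not support that. A TEAE is a statement about timing, and related events have their own tables. The filter is incomplete: it rests on investigator judgment, missing causality is counted as related (SAP 4.7.2), and laboratory tables have none.

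A reader might also infer that the Phase 1 primary objective is distorted. Protocol Table 10 only lists Phase 1 events. Pre-defined unacceptable toxicity is confined to Cycle 1, and both it and the Phase 2 dose decision exclude causes obviously unrelated to isatuximab.

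Finally, transplant in the window may be rare. Protocol 2.1.1 describes waits that often exceed 5 years for sensitised patients, and an E/D visit on days 23 to 37 that is held before surgery would leave at most 7 window days after it. That bears on size. It does not supply the missing split.

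**Conclusion.** The point holds as a gap in reporting. Post-transplant events with onset by day 30 enter the all-causality TEAE and Grade ≥3 tables, and post-transplant laboratory values enter the worst-grade tables where they are recorded. Nothing pre-specified lets a reader separate them.

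The size is unknown and may be zero. It is 8.3, 4.2 or 2.8 percentage points per affected participant at n = 12, 24 or 36, provided that the participant has no event of the same type before transplant. A larger example, such as 2 of 12 participants (16.7 points), is tempting, but the documents give no count to support it. It would also require the post-operative values to be in the database.

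The primary efficacy analysis and the Phase 1 dose decision are not affected. What is affected is the interpretation of the descriptive safety tables.

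**What to change.** Keep last dose + 30 days for the main tables, and add the following to the SAP:

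- **4.1:** flag each AE, laboratory value and PCSA as before or after transplant. The transplant date is already in the eCRF (SAP 4.4.2.1).
- **4.7.2:** repeat the TEAE overview and the Grade ≥3 summary with the window ended the day before transplant. Add a separate AE overview for the time after transplant that includes events within 30 days of the last dose. Show events to day 30 and later events apart, because collection narrows after day 30.
- **4.7.3.1:** repeat the laboratory and PCSA summaries with the same shortened window.

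Separately, reconcile Protocol 7.1.1 with the sections that place the E/D visit before transplant.

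The cost is one flag and one extra set of descriptive tables, with no new data collection. The repeated tables carry slightly less on-treatment time for transplanted participants, and the post-transplant overview may rest on very few people.

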4.2 PARTICIPANT DISPOSITIONS

The number (%) of participants included in each of the analysis populations listed in [Table 3](#) will be summarized.

Screen failures are defined as participants who consent to participate in the study but are not subsequently enrolled. If applicable, the number (%) of screen failures will be provided in the screened population.

Enrolled participants will include screened participants who plan to continue in the treatment phase, ie, those for whom the investigator ticked “Yes” to the question “Will the subject continue in the Treatment phase?” in the Completion of Screening eCRF page.

The number (%) of participants in the following categories will be provided:

- Screened participants, and screen failures (if applicable)
- Enrolled participants

- Enrolled but not treated participants
- Enrolled and treated participants
- Participants who completed the study treatment period as per protocol
- Participants who did not complete the study treatment period as per protocol and main reason for definitive treatment discontinuation
- Participants who completed the site visit follow-up period.
- Participants who did not complete the site visit follow-up period and main reason for site visit follow-up discontinuation
- Participants who completed the study/extended follow-up period.
- Participants who did not complete the study/extended follow-up period and main reason for study/extended follow-up discontinuation
- Participant status at last study contact

If applicable, the number (%) of treated but not enrolled participants will also be presented.

Protocol deviations

Critical and major protocol deviations (automatic or manual) will be summarized in the enrolled and/or treated population.

4.3 PRIMARY ENDPOINT(S) ANALYSIS

4.3.1 Definition of endpoint(s)

The primary endpoint in the Phase 1 portion of the study will focus on safety, ie, AEs/SAEs and laboratory abnormalities. Analysis details of these safety parameters are presented in [Section 4.7.2](#) and [Section 4.7.3.1](#).

In the Phase 2 portion of the study, the primary efficacy endpoint will be RR, to be defined as the proportion of participants meeting at least one of the predefined desensitization efficacy criteria, from baseline up to 26 weeks after treatment period, measured by SAB assay per central laboratory assessment as follows:

- Reduction in cPRA resulting in at least 100% increase of likelihood of finding a compatible donor for target cPRA
- Reduction in antibody titer ($\geq 75\%$ reduction from baseline) to achieve target cPRA
- Elimination of ≥ 1 anti-HLA-antibody (ie, MFI reduced to < 2000) as measured by a SAB assay, for antibodies with baseline MFI ≥ 3000

RR criterion 1: target cPRA

The target cPRA, defined as the reduction of cPRA required to achieve at least 100% increase of likelihood of compatible donor (LCD), is calculated according to the following equation:

$$LCD = 1 \text{ in } \frac{1}{1 - cPRA}$$

Participants with baseline cPRA 100.00% will be assigned with cPRA 99.99% for computational purpose. In addition, cPRA values will be rounded to 2 decimal places prior to LCD calculation ($\geq xx.xx5$ =round up, $< xx.xx5$ =round down).

RR criterion 2: antibody titer

Antibody titer is defined as the last dilution of serum at which positive results is obtained (eg, MFI ≥ 2000). To potentially meet the second RR criterion, serial dilution of the serum collected at baseline is performed until the target cPRA is achieved. If subsequent post-treatment serum is diluted at $\geq 75\%$ reduction from the baseline dilution that achieved target cPRA, and again meet target cPRA anytime within the 26-week post-treatment period, participant will have met RR criterion 2.

RR criterion 3: anti-HLA-antibody

An anti-HLA-antibody is considered to be eliminated if its MFI is reduced to < 2000 at post-treatment. Only antibodies with baseline MFI ≥ 3000 will be included for assessment under this criterion.

4.3.2 Main analytical approach

The primary efficacy analysis is based on a treatment policy estimand introduced in [Section 1.2.1](#).

This primary estimand is defined according to the following attributes:

- The endpoint is RR, as defined in [Section 4.3.1](#).
- The treatment condition of interest is isatuximab
- The analysis population is the efficacy-evaluable population (defined in [Section 3](#))
- The study intervention interruption/discontinuation intercurrent event will be handled with the treatment policy strategy. RR will be assessed based on the 3 criteria irrespective of study intervention interruption/discontinuation.
- Population-level summary will be RR, defined as the proportion of participants meeting at least one of the predefined desensitization efficacy criteria (refer to [Section 4.3.1](#)), along with and two-sided 95% confidence intervals using the Clopper-Pearson method.

Proportion of participants meeting each criterion will also be tabulated.

Calculation details and examples on RR criteria 1 and 2 are provided in Appendix 4, [Section 5.4.2](#) (DESENSITIZATION response criteria).

For RR criterion 3, elimination of anti-HLA-antibody will be determined for each applicable molecular specificity.

